5.2 Primary efficacy outcome

The primary efficacy endpoint of this study is a binary indicator for whether a patient would be alive and free of invasive mechanical ventilation at 28 days. The outcome will be summarized as the proportion of patients alive and free of invasive mechanical ventilation at 28 days and the difference in the proportions between the two study arms will be evaluated with Chi-square test. The odds ratio of being alive and free of invasive mechanical ventilation at 28 days for Dupilumab vs. placebo and its 95% confidence interval (CI) will be estimated in logistic regression, adjusting for potential baseline characteristics if necessary.

5.3 Secondary outcomes

5.3.1 Eosinophilia as the safety outcome: Eosinophilia is a binary indicator for a patient

to have an absolute eosinophil count $> 0.6 \text{ k}/\mu\text{l}$ at ≥ 1 measurement based on the blood counts with differentials and complete metabolic panels on Day 0, 2, 5, 7, 14, 28 and 60 (Data on Day 7, 28 and 60 would be optional). The outcome will be summarized as the proportion of patients with eosinophilia and the difference in the proportions between the two study arms will be evaluated with Chi-square test. The odds ratio of having eosinophilia for Dupilumab vs. placebo and its 95% CI will also be estimated in logistic regression, with adjustment for other covariates.

5.3.2 Other secondary safety and efficacy outcomes:

- Cumulative incidence rate of adverse events (injection site reactions, eye/eyelid inflammation, conjunctivitis, oropharyngeal pain, insomnia, tooth ache, gastritis, arthralgia, bacterial pneumonia, herpes viral infection, hypereosinophilic syndrome, hypersensitivity reaction, other grade 3 or 4 adverse events, serious adverse events or death) is defined as number of adverse events divided by the total number of individuals in the population at risk for the time interval. The rate ratio of adverse events for Dupilumab vs. placebo and its 95% CI will be analyzed in Poisson regression, in which the follow-up time interval will be considered as the offset. Adjusted analysis for other covariates will be performed, as necessary. Mortality at 60 days will be analyzed as the time to event response. Survival probabilities will be estimated by the Kaplan-Meier method, and the difference in the mortality risk between the two treatment groups will be evaluated by the log-rank test and further in Cox regression, adjusting for the baseline covariates. For the analysis of mortality over the first year, additional adjustment for dynamic mechanical ventilation effect will be considered by including being on ventilation as a time-vary covariate in the Cox regression.
- Plasma total Immunoglobulin E (IgE) levels on Day 0 and 14 will be considered as continuous responses, and difference between treatment arms will be evaluated by t-test or Wilcoxon test initially, and adjusted difference and its 95% CI will be estimated from linear regression. Further, changes of IgE from Day 0 to Day 14 will also be explored and the difference between the two study arms will be analyzed similarly.
- Plasma inflammatory markers (C-reactive protein and ferritin) on Day 0, 7 and 14 (Day 7 would be optional if patient discharged) will be analyzed as longitudinal responses in the linear mixed effects model with Dupilumab treatment as a fixed effect. Since this is a randomized study, significant effect of treatment on intercept is not expected. Thus, the longitudinal analysis will focus on the slope difference between the treatment arms via interaction of treatment and time in the model. Since there are only 3 measures for each subject, only random slopes will be specified as *a priori*. Model fitting indices will be examined carefully to ensure the validity of estimated parameters. If Day 7 data won't be available for all patients, these biomarkers between Day 0 to Day 14 will be analyzed as the IgE above.
- Plasma cytokine levels including TARC (CCL17), YKL40, eotaxin 3 (CCL26), IL-13, IL-4, Arg 1, Hyaluronan, soluble ST2 on Day 0, 2, 5, 7, 14, and 28 (Day 7 and 28 optional if patient discharged) will be analyzed as longitudinal responses

in the linear mixed effects model with Dupilumab treatment as a fixed effect, and with appropriate transformation of biomarkers if necessary. The trajectories of these biomarkers will be carefully evaluated, and the slope difference between the treatment arms will be evaluated by the interaction of treatment and time.

Additional curvature in trajectories will also be explored and captured whenever possible in the linear mixed effects model.

- Change in $\text{PaO}_2/\text{SaO}_2$ to FiO_2 ratio on Day 0, 2, 5, 7 (if patient remains inpatient throughout) will be analyzed as longitudinal responses in the linear mixed effects model, similar methods to that for inflammatory biomarkers and cytokine biomarkers as described above.
- All-cause mortality at 28 days will be analyzed as the binary response, using the same methods as that for the primary efficacy outcome and eosinophilia.
- Hospital length of stay (LOS) and ICU LOS between treatment arms will be analyzed as continuous measures using t-test or Wilcoxon test initially, and adjusted difference and its 95% CI will be estimated from linear regression. Since the distributions of hospital LOS and ICU LOS are often skewed, the log-transformed LOS data will be considered in the analyses.
- The response of being alive and free respiratory failure at 28 days is a binary response and will be analyzed using the same methods as that for the primary efficacy outcome.
- The response of being alive and free invasive mechanical ventilation at 60 days is a binary response and will be analyzed using the same methods as that for the primary efficacy outcome.
- National Institute of Allergy and Infectious Diseases (NIAID) 8-point ordinal scale on Day 0, 2, 5, 7, 14, 28, 60, 180 and 360 will be considered as longitudinal data. The distributions of the data will be examined visually first and further collapsing will be considered. Collapsed data will be analyzed in the generalized linear mixed effect model or multinomial logistic regression with the generalized estimating equation approach.
- Proportion of patients alive and free of invasive mechanical ventilation at 60, 90, 120, 150, 180, 270 and 360 days will be estimated from the Kaplan-Meier survival for the time to mechanical ventilation-free survival over the first year. The difference in these proportions between the two treatment groups will be evaluated by the log-rank test and further in Cox regression adjusting for the baseline covariates. For the analysis of mortality over the first year, additional adjustment for dynamic mechanical ventilation effect will be considered by including being on ventilation as a time-vary covariate in the Cox regression.
- Need for vasopressors is a binary response and will be analyzed using the same methods as for the primary efficacy outcome.
- Need for renal replacement therapy is a binary response and will be analyzed using the same methods as for the primary efficacy outcome.
- Need for extracorporeal membrane oxygenation (ECMO) is a binary response and will be analyzed using the same methods as for the primary efficacy outcome.

6.0 Other safety analyses:

Analysis of adverse event (AE) data will primarily be descriptive based on CTCAE coding of events. The proportion of subjects experiencing a severe AE and the proportion experiencing a Grade 3 or higher will be recorded. AE will be compared to published data.

7.0 Sample size estimation and power analysis:

This trial is intended to be an early stage and proof of concept study with the primary goal to collect reliable data and obtain sufficient evidence for future trials. Thus, the emphasis of the study is an exploratory estimation of effect size and incidence of adverse events in terms of eosinophilia; it is not considered as a pivotal trial for efficacy at this time. Therefore, a larger significance level (one-sided alpha=0.1), and the sample size is pre-selected based on the feasibility. Given the current decline trend in the incidence of COVID-19 positive cases, we anticipate to enroll 40 patients realistically into this randomized clinical trial, which shall be sufficient for us to collect reliable and interpretable data for proof of concept to inform future trials. The COVID-19 hospitalization data from our University of Virginia Health System between March 2020 and April 6, 2021 showed that 79.5% of COVID-19 inpatients were alive and free of mechanical ventilation at 28 days under the usual care. With 40 patients that are deemed to be feasible, we would expect Dupilumab to improve a margin of 17.7% in the proportion of patients alive and free of mechanical ventilation at 28 days. That is, it is anticipated that 97.2% of patients being alive and free of ventilation at 28 days in the Dupilumab arm. The power analysis is conducted using the one-sided Score test (Farrington & Manning) with 75% power and 10% type I error.

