2.0 Outcomes

2.1 Primary outcome: The primary efficacy endpoint of this double-blind, placebo-controlled phase IIa trial is a binary indicator for whether a patient would be alive and free of invasive mechanical ventilation at 28 days. The outcome will be summarized as the proportion of patients alive and free of invasive mechanical ventilation at 28 days in those receiving dupilumab in addition to standard of care (treatment arm) compared to those receiving solely standard of care management (placebo arm).

2.2 Secondary outcomes:

2.2.1 Eosinophilia as the safety outcome: The safety endpoint of this study is a binary indicator for whether a patient would have eosinophilia, which is defined as an absolute eosinophil count $> 0.6 \text{ k}/\mu\text{l}$ at ≥ 1 measurement throughout the study period. The outcome will be summarized as the proportion of patients with eosinophilia for treatment arm and placebo arm respectively. Complete blood counts with differentials

and complete metabolic panels will be measured on Day 0, 2, 5, 7, 14, 28 and 60. Day 7, 28 and 60 optional, although recommended, if patient discharged within the time frame.

2.2.2 **Other secondary safety and efficacy outcomes:**

- Cumulative incidence (defined as number of new events divided by the total number of individuals in the population at risk for the time interval) of grade 3 and 4 adverse events, serious adverse events or death including: injection site reactions, eye/eyelid inflammation, conjunctivitis, oropharyngeal pain, insomnia, tooth ache, gastritis, arthralgia, bacterial pneumonia, herpes viral infection, hypereosinophilic syndrome, hypersensitivity reaction.
- Prevalence of B.1.1.7 and B.1.351 and other SARS-CoV-2 lineages in study cohort: Day 0.
- Plasma total Immunoglobulin E (IgE) levels: Day 0 and 14.
- Plasma inflammatory markers (C-reactive protein and ferritin): Day 0, 7 and 14. Day 7 optional if patient discharged.
- Plasma cytokine levels including TARC (CCL17), YKL40, eotaxin 3 (CCL26), IL-13, IL-4, Arg1, Hyaluronan, soluble ST2: Day 0, 2, 5, 7, 14, and 28. Day 7 and 28 optional if patient discharged.
- Change in PaO₂/SaO₂ to FiO₂ ratio: Day 0, 2, 5, 7 (if patient remains inpatient throughout)
- All-cause mortality rate at 28 days.
- Hospital length of stay (LOS)
- ICU LOS
- Proportion of patients alive and free of invasive respiratory failure at 28 days.
- Proportion of patients alive and free of invasive mechanical ventilation at 60 days.

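### The eosinophilia safety endpoint counts the Day 0 value, so eosinophilia already present at baseline scores as an outcome in either arm and on average dilutes the contrast

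*SAP*

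**What the plan says.** The SAP covers the parent trial, HSR 210184. Section 2.2.1 defines eosinophilia as an absolute count above 0.6 k/µl on at least one "measurement throughout the study period". Section 5.3.1 repeats the threshold and makes the indicator "based on the blood counts with differentials and complete metabolic panels on Day 0, 2, 5, 7, 14, 28 and 60". Both sections list Day 0 among the qualifying days. Neither asks for a post-dose value or a patient who was negative beforehand, and the exclusion list in section 1.5 has no eosinophil-count criterion.

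Three of the sampling days are not compulsory. Section 2.2.1 has "Day 7, 28 and 60 optional, although recommended, if patient discharged within the time frame"; section 5.3.1 says only "Data on Day 7, 28 and 60 would be optional".

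The analysis is a crude proportion per arm with a Chi-square test, and then a logistic-regression odds ratio with a 95% interval, adjusted for factors that the section does not name.

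Elsewhere Day 0 is the reference point. For IgE, "changes of IgE from Day 0 to Day 14 will also be explored". For C-reactive protein and ferritin, "Since this is a randomized study, significant effect of treatment on intercept is not expected". Section 2.2.2 defines cumulative incidence of adverse events by new events among those at risk, and section 7.0 names the incidence of eosinophilia as part of what the trial is meant to estimate.

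**The concern.** An indicator that includes Day 0 mixes prevalence at entry with incidence on treatment. A patient already above the threshold is positive whatever happens afterwards and can show nothing about the drug. In expectation such patients add the same share of positives to both arms, so the arms look more alike than they are after dosing. For a safety endpoint that is the less cautious direction, and section 3.3 already records an expectation of no significant difference in eosinophilia.

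The endpoint matters to this trial. Eosinophilia is the first secondary objective (section 1.1), the named safety outcome (section 2.2.1) and the safety measure in the interim look (section 3.3).

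A second, weaker issue sits in the same definition. A rule of at least one positive measurement gives more chances to score to patients who are sampled more often, and the optional visits tie the number of samples to discharge. The SAP has no rule for this: the missing-at-random models in section 8.0 do not act on a crude ever/never indicator.

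**Working it through.** **Inputs from the documents.** 40 patients randomised 1:1, taken as 20 per arm (SAP 1.2); two-sided 5% tests (SAP 3.4); Chi-square and odds ratio for eosinophilia (SAP 5.3.1); six scheduled post-baseline days, of which Days 2, 5 and 14 are not optional.

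**Assumed inputs.** The SAP gives no expected eosinophilia rate, sample size or power. I assume a Day 0 prevalence *b* of 2 to 10%, equal in expectation in both arms, and post-dose risks *p* of 30% (dupilumab) and 10% (placebo) among patients negative on Day 0.

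**Check of the power method.** The SAP's only sizing figure is for the primary endpoint: 79.5% v 97.2%, one-sided 10%, 75% power (section 7.0). Exact enumeration of the pooled score test with 20 per arm gives 75.1%, so the figure reproduces. It says nothing about eosinophilia, but the same enumeration is used below with a two-sided 5% Chi-square without continuity correction.

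**Step 1: effect of counting Day 0.** Scored proportion = *b* + (1 − *b*) × *p*, so the difference shrinks by the factor (1 − *b*).

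| Day 0 prevalence | Placebo | Dupilumab | Difference | Odds ratio | Power |
|---|---|---|---|---|---|
| Day 0 not counted | 10.0% | 30.0% | 20.0 points | (0.30/0.70)/(0.10/0.90) = 3.86 | about 36% |
| 2% | 0.02 + 0.98 × 0.10 = 11.8% | 0.02 + 0.98 × 0.30 = 31.4% | 19.6 points | (0.314/0.686)/(0.118/0.882) = 3.42 | about 33% |
| 10% | 0.10 + 0.90 × 0.10 = 19.0% | 0.10 + 0.90 × 0.30 = 37.0% | 18.0 points | (0.37/0.63)/(0.19/0.81) = 2.50 | about 25% |

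**Step 2: would it arise in 40 patients?** Expected Day 0 positives are 40 × *b*, that is 0.8 to 4. The chance of at least one is 1 − (1 − *b*)^40, that is 55% to 99%.

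**Step 3: what removing Day 0 positives costs.** At 10% prevalence about 20 × 0.90 = 18 patients per arm remain. The same enumeration at 30% v 10% gives about 32% power. So the realistic gain at that prevalence is from about 25% to about 32%, and the odds ratio being estimated returns to 3.86.

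**Step 4: unequal sampling.** With an assumed risk *h* per sample, independent between samples, the chance of scoring in *k* samples is 1 − (1 − *h*)^*k*. At *h* = 5% this is 14.3% for three post-baseline samples and 26.5% for six. That compares two individual patients. For an arm difference, suppose 80% of one arm and 50% of the other skip every optional visit, with equal *h*:

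- 0.80 × 14.3% + 0.20 × 26.5% = 16.7%
- 0.50 × 14.3% + 0.50 × 26.5% = 20.4%

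The spurious gap is about 3.7 points (2.4 at *h* = 3%, 5.9 at *h* = 10%).

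**Step 5: should Days 2, 5 and 14 be the main comparison?** Let 30% v 10% be the risk over six samples with constant risk per sample. Over three samples it is 1 − √0.70 = 16.3% v 1 − √0.90 = 5.1%, a difference of 11.2 points with power about 18%. That is below the 25% left by keeping Day 0 at 10% prevalence. If most optional samples are missed in any case, the loss is smaller.

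**The case against.** The strongest reply is that this is a secondary, exploratory endpoint in a proof-of-concept trial, that the dilution on the planned difference scale is at most 2 points in the example, and that every rate in the example is assumed. Section 5.3.1 plans covariate adjustment, section 4.0 lists baseline blood results among the baseline data, and section 8.0 foresees sensitivity analyses for selected secondary outcomes. Most of this is fair, and it limits the weight of the point. It does not repair the definition. Baseline eosinophil status is not a named covariate, and the crude proportions and Chi-square are untouched by any adjustment.

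It is also fair that the SAP never states that the Day 0 sample precedes the first dose. Its use of Day 0 as baseline elsewhere makes that the natural reading, but it is a reading.

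Timing is a further objection that stands. Protocol section 1.0 says enrolment in the parent trial closed in November 2021 and reports its findings, so a redefinition now is post hoc and must be labelled as such.

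Two stronger readings are tempting, and the documents support neither:

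- A reader might infer that baseline eosinophilia is being attributed to dupilumab. It is not. It scores in both arms of a randomised, placebo-controlled trial, so the expected effect is dilution.
- A reader might infer that earlier discharge on dupilumab hides a signal through fewer samples, perhaps by the 12 points that separate three samples from six. That figure compares a minimally sampled patient with a fully sampled one; a marked imbalance between arms gives about 3.7 points at the same risk per sample. The direction is also open. Protocol sections 1.0 and 3.2 report lower 60-day mortality on dupilumab, and section 6.2 reports 7 deaths among 40. Patients who die give no later samples, so better survival would add samples on dupilumab.

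**Conclusion.** The point holds for Day 0. As written, the rule counts baseline eosinophilia as an outcome, against the SAP's own use of Day 0 as baseline and its stated interest in incidence. The size is modest on the difference scale and larger on the odds ratio: a post-dose contrast of 20 points and odds ratio 3.86 becomes 19.6 to 18.0 points and 3.42 to 2.50 at 2 to 10% Day 0 prevalence. This rests on assumed rates and on equal expected prevalence in the arms. In any one trial of about 20 per arm, chance imbalance in Day 0 positives could move the result either way.

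The optional visits justify reporting and a sensitivity analysis. They do not support a claim about the direction of bias, and they do not justify dropping the optional days from the main comparison.

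**What to change.** 1. In SAP 2.2.1 and 5.3.1, define the endpoint as a first absolute eosinophil count above 0.6 k/µl after the first dose, in patients not above it on Day 0. State whether the Day 0 sample is taken before dosing.
2. Report Day 0 eosinophilia separately by arm.
3. Keep all post-dose days in the main comparison.
4. Tabulate the number of post-dose samples per patient by arm, and add a sensitivity analysis restricted to Days 2, 5 and 14.
5. If the parent-trial analysis has already been run under the existing definition, show both results and label the new one post hoc.

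The cost is a change of definition and a re-tabulation of counts already scheduled, with no added visits or samples. The downside is that patients positive on Day 0 leave the denominator: an expected 0.8 to 4 of 40 under the assumed prevalences.

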1.0 Introduction

1.1 Study objectives: The primary objective is to determine the efficacy of dupilumab use plus standard of care management in patients hospitalized with moderate to severe COVID-19 infection compared to placebo plus standard of care management assessed by the proportion of patients alive and free of invasive mechanical ventilation at 28 days. The secondary objectives are to: (1) evaluate the safety of Dupilumab use in terms of eosinophilia in patients hospitalized with moderate to severe COVID-19 infection, (2) compare clinical outcomes on Dupilumab versus placebo across a range of secondary clinical safety and efficacy domains, and (3) evaluate the immunologic and biologic end points of inhibition of type 2 inflammation.

1.2 Study design: This is a randomized, double-blind, placebo-controlled, superiority phase IIa trial to assess the safety and efficacy of dupilumab use in hospitalized patients with moderate to severe COVID-19 infection. A total of 40 eligible subject will be enrolled and randomized in a 1:1 ratio to receive either dupilumab or placebo, stratifying on the disease severity measured by the required oxygen $\leq 15\text{L}$ or $> 15\text{L}$ by nasal cannula. Both arms will receive standard of care management per current National Institutes of Health (NIH) COVID-19 treatment guidelines (<https://covid19treatmentguidelines.nih.gov/>) in addition to their randomized treatments. Patients will be followed prospectively for up to 60 days after enrollment.

1.3 Database Sources: Completed forms and electronic data will be entered into the data management system in the REDCap platform. Only authorized individuals shall have access to electronic CRFs.

1.4 Randomization:

In this randomized, double-blind, placebo-controlled Phase IIa trial, a total of 40 eligible subjects will be enrolled and randomized in a 1:1 ratio to receive either dupilumab or placebo, stratifying on the disease severity, which is measured by the required oxygen $\leq 15\text{L}$ or $> 15\text{L}$ by nasal cannula. Both arms will receive standard of care management per current National Institutes of Health (NIH) COVID-19 treatment guidelines (<https://covid19treatmentguidelines.nih.gov/>) in addition to their randomized treatments.

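### SAP 5.3.1 analyses the eosinophil count only as ever above 0.6 k/µl, so the size and persistence of a rise are never compared between arms

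*SAP*

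**What the plan says.** SAP 1.1 lists as its first secondary objective to "evaluate the safety of Dupilumab use in terms of eosinophilia". SAP 2.2.1 defines the outcome: "The safety endpoint of this study is a binary indicator for whether a patient would have eosinophilia", where one count above 0.6 k/µl at any time in the study is enough. Counts are scheduled on Days 0, 2, 5, 7, 14, 28 and 60, and those on Days 7, 28 and 60 are optional.

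The analysis is in SAP 5.3.1: "The outcome will be summarized as the proportion of patients with eosinophilia and the difference in the proportions between the two study arms". The comparison is a chi-square test, followed by a logistic odds ratio with 95% CI. The look after 20 patients (SAP 3.3) also uses only the percentage with eosinophilia.

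No section names an analysis of the count itself, its peak, or the time spent above the cut. In SAP 5.3.2, by contrast, IgE is a continuous response with change from Day 0 to Day 14. CRP, ferritin, eight cytokines and the oxygenation ratio go into linear mixed models.

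This SAP belongs to the parent trial (HSR 210184). The supplied protocol is its one-year follow-up and has no eosinophil endpoint.

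**The concern.** A single value of 0.61 k/µl scores the same as counts several times higher at every visit. A clear rise that stays at or below 0.6 k/µl scores the same as no change. The marker chosen to describe safety is thus analysed more coarsely than the other repeated laboratory measures.

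Two things are at stake. First, later trials would learn how often one cut was crossed, but not how far counts rose or for how long. Second, SAP 3.3 already expects no significant difference in eosinophilia. In 40 patients, a non-significant chi-square would fit that expectation whether or not the drug had raised the counts.

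**Working it through.** **Inputs from the SAP.** Section 1.2: "A total of 40 eligible subject will be enrolled and randomized in a 1:1 ratio to receive either dupilumab or placebo", hence 20 per arm. Section 5.3.1: "difference in the proportions between the two study arms will be evaluated with Chi-square test". Section 3.4 sets two-sided 5% for all tests, while section 7.0 uses one-sided 10% for sample size. The SAP does not say that the second level applies to eosinophilia, so both are shown.

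**Assumed, because the documents give no figure.** Placebo rate of eosinophilia 5, 10 or 20%; log counts normal with equal SD; every treated patient shifted up by 0.8 SD.

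**The plan's own power figure.** The SAP gives none for eosinophilia. For the primary endpoint it states 75% (79.5% vs 97.2%, one-sided 10%, score test). Exact binomial enumeration with 20 per arm gives 75.1%, so the method reproduces the plan's figure.

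**Step 1, treated rate.** With cut z = Φ⁻¹(1 − pC), the treated rate is pT = 1 − Φ(z − 0.8).
- pC 5%: z = 1.645, pT = 1 − Φ(0.845) = 19.9%
- pC 10%: z = 1.282, pT = 1 − Φ(0.482) = 31.5%
- pC 20%: z = 0.842, pT = 1 − Φ(0.042) = 48.3%

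**Step 2, yes/no analysis.** Sum the binomial probabilities of all outcomes (x placebo events, y treated events) for which Z = [(y − x)/20] / √[p̄(1 − p̄)(2/20)], with p̄ = (x + y)/40, passes the critical value. That is |Z| > 1.96 for two-sided 5%, or Z > 1.282 for one-sided 10%.

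**Step 3, the count itself.** For a t-test on one log value per patient, the noncentrality is 0.8 × √(20/2) = 2.53 with 38 df. The critical value is 2.024 (two-sided 5%) or 1.304 (one-sided 10%).

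| Placebo rate | Yes/no, two-sided 5% | Count, two-sided 5% | Yes/no, one-sided 10% | Count, one-sided 10% |
|---|---|---|---|---|
| 5% | 29% | 69% | 60% | 89% |
| 10% | 40% | 69% | 67% | 89% |
| 20% | 49% | 69% | 77% | 89% |

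The gap is about 20 to 40 points at two-sided 5% and about 12 to 29 points at one-sided 10%.

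**Step 4, precision.** At an assumed 10% vs 30%, the 95% CI half-width for the risk difference is 1.96 × √(0.1 × 0.9/20 + 0.3 × 0.7/20) = 0.24, or about 24 points either way.

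**Step 5, repeated counts.** Step 3 uses one value per patient, so it does not describe a repeated-measures analysis. A simulation of seven visits comes closer. It assumes within-patient correlation 0.5, an effect building to 0.8 SD by Day 14, and 10% of placebo patients ever above the cut, which gives 28% of treated patients. Power at two-sided 5% was 33% for the yes/no outcome, 60% for the peak count and 89% for the Day 0-adjusted mean log count. With half the patients missing the optional visits it was 23%, 42% and 75%.

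**Step 6, a different response pattern.** Suppose only 30% of treated patients respond, each by 2.5 SD, with a 5% placebo rate (two-sided 5%). Simulated power is then about 52% for chi-square, 43% for the t-test and 33% for Wilcoxon. With a 10% placebo rate it is about 45%, 42% and 32%. The advantage of a single-value comparison disappears or reverses.

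**The case against.** **The plan meets its stated aim.** A reader might infer that 5.3.1 contradicts SAP 7.0. It does not. Section 7.0 puts the emphasis on effect size and on the incidence of adverse events in the form of eosinophilia. An incidence is a proportion, and 5.3.1 delivers it.

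**A rise in counts is not harm.** A reader might also infer that the trial gives up power to see harm. The documents do not say that a rise below 0.6 k/µl is harmful, so the calculation concerns a laboratory marker only. Extreme rises are partly covered elsewhere: SAP 2.2.2 lists "hypereosinophilic syndrome, hypersensitivity reaction" among the adverse events, and 5.3.2 analyses these by Poisson rate ratio. That still counts events and would not describe moderate rises.

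**The size depends on the model.** This stands. A uniform shift favours the comparison of counts, and Step 6 shows the opposite case. The documents cannot say which pattern applies.

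**The general strategy may already cover it.** SAP 5.1 plans trajectories and mixed models for immune biomarkers in general. But no biomarker list includes eosinophils, and 5.3.1 sets out its own method. If they were meant to be included, a sentence should say so.

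**The trial is exploratory.** SAP 5.1 says that formal testing is not the goal, which makes power a weak yardstick. It also strengthens the case for estimating the size of a rise with a confidence interval.

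**Timing.** The protocol's Summary says parent enrolment closed in November 2021 and already reports the safety and mortality conclusions. An addition made with results known is post hoc.

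**Conclusion.** The point holds as a gap in the safety analysis that is cheap to fill. It is not an error in the yes/no endpoint, nor a conflict with SAP 7.0. As written, neither the size nor the persistence of an eosinophil rise is compared between arms, although repeated counts are scheduled.

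That part rests on the text alone. The power part is conditional on 20 per arm, normal log counts with equal SD, a uniform 0.8 SD shift and placebo rates of 5 to 20%. Under these the yes/no analysis can have much lower power to detect a rise, by an amount that depends on the significance level. It should not be quoted as a fixed loss: with strong response in a minority of patients, a single-value comparison may show no gain.

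**What to change.** Keep the yes/no endpoint and the 0.6 k/µl cut. Add to SAP 5.3.1, labelled supportive and exploratory:

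- A repeated-measures model of log post-baseline eosinophil counts, with a small constant fixed in advance for zeros. Terms: arm, visit, arm-by-visit and the Day 0 count.
- One named overall contrast: the average post-baseline ratio of geometric means, dupilumab to placebo, with 95% CI. Ratios by visit are descriptive.
- A table by arm of each patient's highest post-baseline count and the number of visits above 0.6 k/µl out of visits sampled. The denominator is needed because Days 7, 28 and 60 are optional.
- A statement that the model relies on SAP 8.0's missing-at-random assumption, with the number of patients sampled at each visit. Protocol 6.2 reports 7 of 40 patients dead by Day 60, so late counts come from survivors.

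The cost is one paragraph, one model and one table on counts already scheduled. The downside is one more exploratory result, to be labelled post hoc if it is added after the parent-trial results are known. No clinical rule changes.
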